8.2.9 Rezūm II Study: Conclusion

The convective water vapor energy ablation of prostate adenomas with the Rezūm System demonstrated statistically significant and clinically meaningful improvements in the symptoms for LUTS due to BPH as early as within 2 weeks after treatment. The clinical efficacy and safety were durable over 24 months with improved symptoms, flow rate, QoL, decreased incontinence episodes and preserved sexual function. These results support the application of WAVE technology as a safe and effective minimally invasive therapeutic alternative for symptomatic BPH without compromising sexual function including treatment of patients with a median lobe.

9 Rezūm XL Clinical Study Design

This is a prospective, multicenter, single arm clinical trial designed to evaluate the safety of the Rezūm System in treating subjects with symptomatic BPH for prostate sizes $>80\text{cm}^3$ and $\leq 150\text{cm}^3$.

A total of 88 subjects will be enrolled in the study. After the completion of the 6-month follow-up evaluation a responder analysis will be completed based on baseline IPSS (responder) at 6 months post-procedure.

Subjects with signed informed consents and who meet all the inclusion and none of the exclusion criteria will be enrolled to receive convective water vapor ablation treatments using the Rezūm System.

[figure not shown]

FIGURE 9-1: STUDY DESIGN FLOW CHART

9.1 Screening and Enrollment

Subjects who give written informed consents to undergo screening procedures will be considered screened subjects. These subjects will undergo a series of baseline screening evaluations. The subjects will be required to meet all inclusion/exclusion criteria prior to enrollment.

Test results that are within the timeframes specified in this protocol may be used. Research coordinators will review questionnaires for completeness only. If a question is left unanswered or is un-interpretable, the coordinator will return the questionnaire to the subject to complete or for clarification at the time of the visit.

Subjects meeting all study inclusion/exclusion criteria after their baseline evaluation will be enrolled upon insertion of the Rezūm delivery device at the time of the Rezūm procedure. Only enrolled subjects constitute the ITT analysis population and will be considered evaluable. Those subjects who do not meet inclusion/exclusion criteria after the screening or baseline evaluation will be counted as screen failures and will be withdrawn from the study provided any screening evaluation related AEs occurring during baseline testing have been resolved.

To access long-term efficacy, all subjects receiving the Rezūm treatment will be monitored for AEs and IPSS assessment for 3 years post procedure.

9.2 Investigational Sites, Sample Size and Study Duration

The study will have up to 11 sites activated. If non-US sites are recruited into the study, a maximum of 1 site outside of the US will be allowed in the study. This non-US sites will be from Australia. A site is considered authorized to enroll subjects after IRB/EC approval(s) are received, all training has occurred, and the study-specific regulatory documents are completed. A site will be considered one of the 11 clinical investigation sites if it is active, which is defined as having subject(s) enrolled. Sites who are authorized to enroll subjects, but do not enroll any subjects, may be replaced and will thereafter not be considered as one of the 11 clinical investigation sites. No one site may enroll more than 33% of the total study sample size.

The maximum size of the study will not exceed 88 subjects. The estimated study duration is 4 years, comprised of 6 months for enrollment, 3 years of follow-up, and 6 months to complete data collection / analysis and compile the final study report.

9.3 Study Objective and Endpoints

The purpose of the study is to determine the safety and efficacy of the Rezūm System in prostate sizes $>80\text{cm}^3$ and $\leq 150\text{cm}^3$. Data from this study will be used to support the expanded indication labeling application for the device in the U.S. and other countries. The endpoints studied to meet these objectives are described below.

9.3.1 Primary Efficacy Endpoint

For the primary efficacy endpoint to be met, the proportion of the modified intention-to-treat analysis population that responds to therapy must be statistically significantly greater than 50%. A responder is defined as a subject who has an IPSS improvement $\geq 30\%$ post-treatment compared to baseline.

9.3.2 Primary Safety Endpoint – Post Procedure Device Related Serious Complications

For the primary safety endpoint to be met, the proportion of the treated analysis population that experiences a safety composite event must be statistically significantly less than 12%.

These composite device-related serious complications for this endpoint are defined as:

- Perforation of the rectum or GI tract
- Formation of fistula between the rectum and urethra
- Permanent damage to the bladder, trigone or ureteral orifices requiring intervention
- Grade 2 hydronephrosis

9.3.3 Safety Monitoring Early Stopping Rule

An early stopping rule is instituted in the study to monitor the rate of steam-related injury.

This early stopping rule is intended to provide a higher degree of sensitivity to steam-related injury and earlier time-frame than is provided by the primary safety endpoint composite which includes a wider spectrum of adverse events and a longer time period of 6-months post-procedure.

If 2 patients experience a post-procedure CEC-determined device-related steam-related injury requiring intervention within the first 20 subjects treated with Rezūm, the early 6 week post procedure stopping rule is triggered. A threshold of 2 patients with an event out of the first 20 subjects is an observed event rate of 10%.

For the study stopping rule “Intervention” is defined as any surgical procedure or hospitalization performed to remedy or correct a potential permanent damage to the bladder, trigone or ureteral orifices, perforation of the rectum or GI tract, or formation of fistula between the rectum and urethra or bladder.

Irrigation of clot retention or necrotic tissue obstruction is allowed, if medically necessary, and should be reported as an adverse event but will not be counted toward the stopping rule.

9.3.4 Secondary Endpoints

The following secondary endpoints will be statistically assessed to provide additional characterization of the Rezūm System in the treatment of obstructive BPH. Secondary endpoint S2 with prespecified hypotheses and well-controlled Type I error will be used to and to support potential labeling claims. Refer to Section 12.4 for further details.

- Secondary Endpoint S1: Device-related retention catheterization rate
- Secondary Endpoint S2: Absolute IPSS improvement at 6 months
- Secondary Endpoint S3: Percent Responder at 1 year
- Secondary Endpoint S4: Percent Responders at 2 years
- Secondary Endpoint S5: Percent Responders at 3 years

9.3.5 Ancillary Endpoints

The following ancillary endpoints are to provide additional characterizations of the safety and effectiveness of the Rezūm System in the treatment of obstructive BPH. Refer to Section 12.5 for further details.

- Ancillary Endpoint A1: Additional Responder Analyses
- Ancillary Endpoint A2: Change in Qmax and PVR
- Ancillary Endpoint A3: Change in Sexual Function
- Ancillary Endpoint A4: Change in Quality of Life
- Ancillary Endpoint A5: Procedure Parameters
- Ancillary Endpoint A6: PGI-I Questionnaire
- Ancillary Endpoint A7: Rezūm II Comparisons

9.4 Subject Selection

To be eligible for enrollment in the study, subjects must meet all of the inclusion criteria and none of the exclusion criteria.

9.4.1 Inclusion Criteria

1. Male subjects ≥ 50 years of age who have symptomatic BPH.
2. International Prostate Symptom Score (IPSS) score ≥ 13 .
3. Peak urinary flow rate (Qmax): ≥ 5 ml/sec to ≤ 12 ml/sec with minimum voided volume of ≥ 125 ml.

4. Post-void residual (PVR) ≤ 300 ml.
5. Prostate volume > 80 cm³ to ≤ 150 cm³

9.4.2 Exclusion Criteria

Urology

1. Any prior invasive prostate intervention (e.g., “Radiofrequency” thermotherapy, balloon, microwave thermotherapy, “Prostatic Urethral Lift”, “Transurethral Resection”, or laser) or other surgical interventions of the prostate.
2. Undergone a prostate biopsy within 60 days prior to the scheduled treatment date or has an imminent need for surgery.
3. Verified acute bacterial prostatitis within last 12 months documented by culture.
4. Active or history of epididymitis within the past 3 months.
5. Urethral strictures, bladder neck contracture, unusual anatomy or muscle spasms that would prevent the introduction and use of the Rezūm device.
6. Diagnosed bladder, urethral or ureteral stones or active stone passage in the past 6 months, provided that stones that are known to be in the kidney and have been stable for a period exceeding 3 months are permissible.
7. Subject interested in maintaining fertility.
8. Use of the following medications where the dose is not stable (stable dose defined as the same medication and dose in the last three months):
 - a. Beta-blockers;
 - b. Anticonvulsants;
 - c. Antispasmodics;
 - d. Antihistamines;
 - e. Alpha blockers for BPH and anticholinergics or cholinergics;
 - f. Type II, 5-alpha reductase inhibitor (e.g., finasteride (Proscar, Propecia));
 - g. Dual 5-alpha reductase inhibitor (e.g., dutasteride (Avodart));
 - h. Estrogen, drug-producing androgen suppression, or anabolic steroids;
 - i. PD5 Inhibitors (e.g., Viagra, Levitra or Cialis)
9. Subjects who have had an incidence of spontaneous urinary retention either treated with indwelling transurethral catheter or suprapubic catheter 6 months prior to baseline. A provoked episode now resolved is still admissible.
10. Evidence of atonic neurogenic bladder evaluated by a baseline urodynamic assessment.
11. Visible hematuria with subject urine sample without a known contributing factor.
12. Presence of a penile implant or stent(s) in the urethra or prostate.
13. Active urinary tract infection by culture within 7 days of treatment or two documented independent urinary tract infections of any type in the past 6 months.

Gastroenterology

14. Previous pelvic irradiation or radical pelvic surgery.
15. Previous rectal surgery (other than hemorrhoidectomy) or known history of rectal disease.

Nephrology

16. Compromised renal function defined as serum creatinine > 2.0 mg/dl.
17. Hydronephrosis (Grade 2 or higher).

Oncology

18. Prostate cancer testing:

If PSA is > 2.5 ng/ml and ≤ 10 ng/ml with free PSA $<25\%$, prostate cancer for the subject must be/had been ruled out through a negative biopsy prior to enrollment.

- Males 50-59 years - PSA is >2.5 ng/ml and ≤ 10 ng/ml with free PSA $<25\%$,
- Males 60+ years - PSA is >4 ng/ml and ≤ 10 ng/ml, with free PSA $<25\%$

19. History of confirmed malignancy or cancer of the prostate or bladder; however, high grade prostatic intraepithelial "PIN" is acceptable.

20. History of cancer in non-genitourinary system that is not considered cured (except basal cell or squamous cell carcinoma of the skin). A potential participant is considered cured if there has been no evidence of cancer within five years of enrollment.

Cardiology

21. History of clinically significant congestive heart failure (i.e., NYHA Class III and IV).

22. Cardiac arrhythmias that are not controlled by medication and/or medical device.

23. An episode of unstable angina pectoris, a myocardial infarction, transient ischemic attack, or a cerebrovascular accident within the past six months.

Pulmonology

24. History of significant respiratory disease where hospitalization for the disease is required.

Hematology

25. Diagnosed or suspected bleeding disorder, or coagulopathies.

26. Use of antiplatelet or anticoagulation medication except for low dose aspirin (<100 mg/day) within 10 days prior to treatment.

Endocrinology

27. History of diabetes not controlled by a stable dose of medication over the past three months, provided that patients with a hemoglobin A1c $<8.0\%$ are allowed.

Immunology

28. History of immunosuppressive conditions (e.g., AIDS, post-transplant).

Neurology

29. Any cognitive or psychiatric condition that interferes with or precludes direct and accurate communication with the study investigator regarding the study or affect the ability to complete the study quality of life questionnaires.

30. Diagnosed or suspected primary neurologic conditions such as multiple sclerosis or Parkinson's disease or other neurological diseases known to affect bladder function, sphincter function or poor detrusor muscle function ($<25\%$ of accepted and established nomograms).

General

31. Currently enrolled in any other pre-approval investigational study in the US (does not apply to long-term post-market studies unless these studies might clinically interfere with the current study endpoints (e.g., limit use of study-required medications, etc.)

32. Any significant medical history that would pose an unreasonable risk or make the subject unsuitable for the study.

33. Inability to provide a legally effective "Informed Consent Form" and/or comply with all of the required follow-up requirements.

9.5 Site Selection

Sites will be selected based on the availability of the subject pool to be included in the study and the sites' ability to perform the research in compliance with FDA IDE regulations and guidelines.

The sites and physicians are required to comply with the FDA's IDE regulations (the definition of subject enrollment is per this protocol). In addition, the sites must be able to comply with any country-specific requirements as well as other requirements specified by their respective IRB or EC.

9.6 Physician Selection

Physicians selected must have experience in performing cystoscopies, treating BPH subjects and/or other male urological therapies. Selected physicians will be trained through the commercial training program in the use of the Rezūm System prior to enrolling subjects. The primary investigator will ensure that only trained sub-investigators who satisfy the physician selection criteria can perform any part of the study interventional procedure.

Healthcare professionals or site staff that assist or perform the follow-up evaluations are not required to be trained on the use of the Rezūm System, but must be delegated and trained to perform the follow-up visit procedures.

10 Study Procedures

10.1 Pre Screening, Screening, and Baseline

An investigational site may pre-screen potential subjects by reviewing medical records to identify the study population. Once identified, these subjects can be approached for the study and consented. The site may not initiate any study-specific (non-standard of care) procedures without first obtaining an informed consent.

All baseline testing and evaluations must be done as close to the time of treatment as possible and repeated if needed. Any required procedures that were performed before obtaining an informed consent as part of the standard of care may be used in lieu of the study tests as described in Table 10-1.

The following evaluations will be completed for all study candidates. Evaluations performed within the screening window may be acceptable. The required baseline evaluations are shown below:

TABLE 10-1: SCREENING EVALUATIONS CONDITIONS

Evaluations	Accepted interval prior to procedure (unless specified otherwise)	Condition
TRUS	Within 6 months of consent	Evaluation is complete and adequately documented in report for assessment.
TAUS	Within 6 months of consent	Evaluation is complete and adequately documented in report for assessment.

Evaluations	Accepted interval prior to procedure (unless specified otherwise)	Condition
Retroperitoneal ultrasound (renal and bladder)	Within 6 months of consent	Evaluation is complete and adequately documented in report for assessment.
Digital rectal exam (DRE)	Within 30 days	Evaluation is complete and adequately documented in report for assessment.
PSA level	Within 180 days of consent	Males 50-59 – If PSA is >2.5 ng/ml and <10 ng/ml with free PSA <25% Males 60+ - If PSA is >4 ng/ml and <10 ng/ml , with free PSA <25%
Prostate biopsy for cancer	Within 12 months	For men with a history of elevated PSA (defined above by age), prostate cancer must be ruled out by a negative biopsy.
Medical history	Within 30 days	Evaluation is complete and adequately documented in report for assessment.
Physical exam evaluation	Within 30 days	Evaluation is complete and adequately documented in report for assessment.
Uroflowmetry 
 • Voided volume (must be ≥ 125 mL or test must be repeated for all the uroflow tests) • Voiding time • Peak flow rate (Qmax)¹ • Average flow rate 	Within 60 days	Must be performed before cystoscopy or ≥ 14 days after cystoscopy and no evidence of UTI.
Post-void residual urine volume (PVR; may be measured by either ultrasound or catheterization but the same method must be used pre- and post-treatment)	Within 60 days of treatment	Must be performed before cystoscopy or ≥ 14 days after cystoscopy and no evidence of UTI. The PVR method used during screening must be the same as that used in the follow-up tests.
Blood analysis 
 • Complete blood cell count (CBC) • Blood urea nitrogen (BUN) • Blood sugar • Serum creatinine 	Within 30 days	
Urine analysis 
 • Sugar • Protein • WBC/RBC • Bacteria 	Within 30 days	

Evaluations	Accepted interval prior to procedure (unless specified otherwise)	Condition
Urine culture for infection only if infection is suspected		Must have documented negative infection before enrolling and before taking the IPSS at baseline.
Urodynamic Testing	Within 60 days	The Urodynamic guidelines provided by the study sponsor must be used by all participating sites.
Subject questionnaires 
 • International Prostate Symptoms Score (IPSS) – Standard • BPH Impact Index (BPHII) • MSHQ-EjD • International Index of Erectile Function (IIEF) • EQ-5D-5L • Pain Scale 	Within 30 days	
Screening flexible cystoscopy (recorded)	Within 60 days	
Current or prior (up to 6 months) medication consumption	Prior to enrollment	A list of current and prior medication is required to determine the need for wash in and stability of dose.
Note: ¹ Due to the variability of the uroflow study, only whole numbers for Qmax will be used. Fractions will be rounded to the nearest whole number following conventional rounding rules.		

10.2 Subject Enrollment

Only subjects who meet all the inclusion and none of the exclusion criteria will be eligible to be enrolled and participate in the study. A subject will be considered officially enrolled only if the subject has signed an informed consent, meets all the inclusion and none of the exclusion criteria and at the time of the Rezūm Delivery device insertion into the urethra.

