17.2 Subject Enrollment Process

All study candidates, after pre-procedure screening, must appropriately consent to participate in the study, as administrated by qualified study site personnel using an IRB and Sponsor-approved ICF prior to beginning any aspect of the study procedure or tests that are not standard of care for the site. Investigational sites will be required to document the consent process within each enrolled subjects medical record. Administering the questionnaires can be done prior to signing the ICF. Only subjects who meet the inclusion/exclusion criteria, who signed the study informed consent and completed device insertion will be considered enrolled in the study.

Timely communication by each site is critical to avoid over enrolling when the enrollment is close to the end of each phase. When enrollment is close to the end of each phase, the following procedures may be implemented:

- Before the subject signs the study ICF, the Study Coordinator must confirm the availability of an enrollment slot. A phone call to the Sponsor is the preferred method.
- Immediately after the procedure, the Study Coordinator must inform (phone call or fax or e-mail) the Sponsor to confirm the subject's eligibility and the completion of the procedure. A phone call to the Sponsor is the preferred method.

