17.8.3 Protocol Deviations

A protocol deviation/violation is generally an unplanned excursion from the protocol that is not implemented or intended as a systematic change. An investigator who failed to perform tests or examinations as required by the protocol, or failures on the part of study subjects to complete scheduled visits as required by the protocol, would be considered protocol deviations. These type of deviations are reported to the Sponsor in accordance with the IRB policy.

A Protocol Deviation CRF must be completed by the site for each study protocol deviation (e.g., failure to obtain informed consent, enrolling a subject who does not meet inclusion/exclusion criteria, not performing required testing, missed follow-up window, etc.). An Investigator must notify the Sponsor and the reviewing EC/IRB of any deviation from the Study Protocol that was done to protect the life or physical well-being of a subject. Such notice should be given as soon as possible, but no later than five (5) working days after the event occurred.

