17.8.4 Protocol Deviation Notification/Approval to IRB/Sponsor before Implementation

A protocol deviation may be a limited prospective exception to the protocol (e.g., agreement between Sponsor and Investigator to enroll a single subject who does not meet all inclusion/exclusion criteria due to out of window historical data). Deviations initiated by the clinical investigator must be reviewed and approved by the IRB and the Sponsor prior to implementation. This type of deviation can be used for historical data that is out of window due to medication washout or date of screening visit. The objective is to prevent subjects from being subject to repeat and possible invasive testing. These type of deviations are only approved if they do not impact data integrity or put subjects at unreasonable risk.

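### The plan ties the ITT set to meeting every eligibility criterion in some sections and treats ineligible men as enrolled in others, so the primary efficacy denominator is not fixed

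*Combined protocol and SAP*

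**What the plan says.** Three sections of the protocol define enrolment, and each includes eligibility.

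- Section 10.2: a man is "officially enrolled only if the subject has signed an informed consent, meets all the inclusion and none of the exclusion criteria", with the status tied to the moment the delivery device enters the urethra.
- Section 17.2: "Only subjects who meet the inclusion/exclusion criteria, who signed the study informed consent and completed device insertion will be considered enrolled in the study".
- Section 9.1: "Subjects meeting all study inclusion/exclusion criteria after their baseline evaluation will be enrolled upon insertion of the Rezūm delivery device".

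Section 9.1 then turns enrolment into the analysis set: "Only enrolled subjects constitute the ITT analysis population and will be considered evaluable".

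Three other sections assume that ineligible men can be enrolled or have data in the analysis.

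- Section 17.8.3 lists "enrolling a subject who does not meet inclusion/exclusion criteria" among the protocol deviations to be recorded.
- Section 17.8.4 allows, as a limited prospective exception, an "agreement between Sponsor and Investigator to enroll a single subject who does not meet all inclusion/exclusion criteria due to out of window historical data". Both IRB and sponsor must approve, and only if data integrity and subject safety are not compromised.
- Section 10.8.2.2 lets the CEC exclude a man's data for any of seven listed failures found later. The exclusion is optional.

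The synopsis and 12.1 test primary efficacy in the ITT set. Section 9.3.1 says modified intention-to-treat and does not define the modification. Primary safety (9.3.2) and the secondary endpoints (12.4) use treated men.

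**The concern.** The sections give different answers about a man who was treated but did not meet a criterion. Under the literal wording of 10.2 and 17.2 he was not enrolled and so is outside ITT. Under 17.8.3 he is enrolled, with a deviation. Under 10.8.2.2 he is in the data unless the failure is one of the seven listed and the CEC removes him. A man admitted under 17.8.4 is knowingly enrolled there, yet fails the 10.2 definition outright.

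This matters because primary efficacy is an open-label, single-arm count against 50%, so each man left out moves the result. There is no spare sample: 12.1 requires at least 88 ITT men and 9.2 caps the study at 88.

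Faults may also come to light late. Section 18.1.1 lists checking that subjects met the enrolment criteria among the monitors' possible activities. The only visit timing it anticipates for each site is at least one visit once all 6-month follow-ups there are complete, when the primary outcome is known. Some boundaries are themselves unclear: the upper Qmax limit includes 12 ml/sec in 9.4.1 and excludes it in 11.3, and Table 10-1 rounds Qmax to whole numbers. Those two passages need reconciling. If ineligibility is looked for more closely in men who do badly, removing them favours passing.

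**Working it through.** **Inputs.** From 12.1 and 12.3: exact one-sample binomial test, p0 = 0.50, one-sided alpha 0.025, assumed responder rate 0.675, power 90%, N = 88. From 9.2: maximum 88 subjects. The documents give no rate of ineligible enrolment, so the number dropped, k, is an assumption, shown from 0 to 6 of 88 (6/88 = 6.8%). I take 88 men as treated and none replaced.

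**The plan's own figure.** The pass mark is the smallest c with P(X ≥ c | n, 0.5) ≤ 0.025. For n = 88, c = 54 (54/88 = 61.4%), with exact alpha 0.0211 and power 0.909 at 0.675. The 67.5% agrees with the Clopper-Pearson 99% lower limit for 106/136, 0.6751. The stated sample size reproduces.

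**Results that change with the denominator** (p = P(X ≥ x | n, 0.5); the k men dropped are all non-responders):

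| k | Responders | All 88 | After dropping k |
|---|---|---|---|
| 2 | 53 | 53/88 = 60.2%, p = 0.0347, fails | 53/86 = 61.6%, p = 0.0199, passes |
| 4 | 52 | 52/88 = 59.1%, p = 0.0546, fails | 52/84 = 61.9%, p = 0.0188, passes |
| 5 | 51 | 51/88 = 58.0%, p = 0.0827, fails | 51/83 = 61.4%, p = 0.0238, passes |

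**Error and power over repeated trials.** Worst case: every dropped man is a non-responder, so the error at a true 50% is P(X ≥ c(88 − k)) with X ~ Bin(88, 0.5). Neutral case: dropping is unrelated to response, so error and power are those of an ordinary trial of 88 − k men.

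| k | n | c | Worst-case error | Neutral error | Neutral power at 0.675 |
|---|---|---|---|---|---|
| 0 | 88 | 54 | 0.0211 | 0.0211 | 0.909 |
| 1 | 87 | 54 | 0.0211 | 0.0157 | 0.883 |
| 2 | 86 | 53 | 0.0347 | 0.0199 | 0.898 |
| 3 | 85 | 53 | 0.0347 | 0.0147 | 0.870 |
| 4 | 84 | 52 | 0.0546 | 0.0188 | 0.886 |
| 5 | 83 | 51 | 0.0827 | 0.0238 | 0.901 |
| 6 | 82 | 51 | 0.0827 | 0.0176 | 0.873 |

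The neutral error never exceeds 0.024, and power stays at about 0.87 to 0.90. Inflation needs the dropped men to be mainly non-responders.

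**The case against.** The best reply is that eligibility is a gate passed once. Section 9.1 places the judgement after the baseline evaluation and enrolment at insertion, and it calls men who fail at that stage screen failures. Section 10.2 also refers to the time of insertion. No section says that a treated man found ineligible later was never enrolled. Section 10.8.2.2 is a specific rule for late findings, in the hands of three independent physicians (19.1), and it would be pointless if such men left ITT automatically. Baseline uroflowmetry and TRUS are interpreted by the principal investigator for eligibility (11.3.2, 11.6), so a later independent reading is not the stated eligibility test. The 17.8.4 exception is narrow: its example is out-of-window historical data.

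Much of this stands. A reader might infer that the plan automatically removes from ITT any treated man found to breach a criterion. The documents do not support that as the only reading. Nor do they support saying that the error rate is in fact inflated. At a true 50% rate, with dropping unrelated to response, the chance that all dropped men are non-responders is 0.5² = 25% for 2 men, 0.5⁴ = 6% for 4 and 0.5⁶ = 1.6% for 6.

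The reply does not remove the conflict. Sections 10.2 and 17.2 state eligibility as a fact about the man, not as a judgement made at baseline. A man enrolled under 17.8.4 is known before treatment to miss a criterion, so even the gate reading excludes him. Section 9.3.1 leaves open which set is tested. The 10.8.2.2 rule is not required to be applied without knowledge of outcome.

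**Conclusion.** The concern holds as an unresolved definition of the primary efficacy set. The sections can be read to keep or to remove a treated man who breaches a criterion, and nothing in the text supplied decides between the readings. The enrolment wording affects primary efficacy only.

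In a close result, two ineligible non-responders are enough to turn a fail at 53/88 into a pass at 53/86. The error figures of 0.035 (2 dropped), 0.055 (4) and 0.083 (5 or 6) are upper limits for those counts, which rest on two assumptions: the number dropped, and that all of them are non-responders. If dropping is unrelated to response, the error stays within the nominal 0.025 and only a little power is lost.

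One limit remains. Section 10.6 refers to a separate SAP (CLP 3034-002), there for missing data. Its text was not available, so a population definition in it could not be checked. The protocol's own sections would still need to agree.

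**What to change.** - In 9.1, 10.2 and 17.2, define enrolled and ITT as every consented man in whom the delivery device is inserted, regardless of any later eligibility finding. Keep the criteria as the rule for who should be enrolled, not for who is analysed.
- In 9.3.1, name that same set in place of the undefined modified ITT, in line with the synopsis and 12.1.
- Record every eligibility breach as a deviation under 17.8.3, and state that men admitted under 17.8.4 are in the ITT set.
- In 10.8.2.2, confine the eligibility exclusions, other than lack of consent, to a sensitivity analysis, with each decision made without knowledge of the man's IPSS outcome. Without this change, men could still be removed after outcomes are known.
- Check that CLP 3034-002 uses the same definition.

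The cost is wording in five sections and one sensitivity analysis. The design figures do not change: N = 88, 54 responders to pass, exact alpha 0.0211, power 0.909. The downside is that a few ineligible men stay in the denominator, so the responder rate may be slightly lower.
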